### 6.5.3.2 Selumetinib Supportive Care

- **Hypertension:** It is recommended that additional blood pressure monitoring occur for participants who may be at risk (participants with hypertension at baseline) or those with antecedents of hypertension or those treated with antihypertensive medication. Early initiation of treatment is recommended after diagnosis, with aggressive management of emergent hypertension.
- **Nausea and/or vomiting:** Because nausea and vomiting have been reported for selumetinib, it is recommended that participants are educated on the possibility of occurrence of these side effects prior to starting study treatment. Participant education as well as proper management of nausea and/or vomiting at the first sign is important. Clinical judgment and experience of the treating physician should guide the management plan of each participant. Participants experiencing nausea and/or vomiting CTCAE Grade  $\geq 1$  should receive antiemetics at the discretion of the treating physician (as per local guideline). It is recommended that participants be provided a prescription for antiemetics, and are instructed on the use of antiemetics on the first day of study drug treatment. Prophylactic antiemetics such as dexamethasone 8 mg, prochlorperazine, or metoclopramide may be administered to participants on an "as needed" basis. Medication use should be recorded accordingly.

Dose interruption/reduction decisions for nausea and/or vomiting should be based on the CTCAE grade of the toxicity and the guidelines provided in Section 6.6.4.

As guidance for recommendations on supportive measures for the prevention and/or management of nausea and/or vomiting, the published recommendation from ASCO [Sepulveda, A. R., et al 2017], European Society for Medical Oncology (ESMO) [Van Cutsem, E., et al 2016], and Multinational Association of Supportive Care (MASCC) can be used [Basch, E., et al 2011] [Roila, F., et al 2010].

- **Diarrhea:** Management of diarrhea should be instituted at the first sign of abdominal cramping, loose stools or overt diarrhea. All concomitant therapies used for treatment of diarrhea must be recorded on the Concomitant Medications section of the participant record. It is recommended that participants be provided loperamide tablets and are instructed on the use of loperamide on the first day of selumetinib treatment. In addition to the selumetinib -induced diarrhea dosing guidelines, these instructions should be provided at each visit and the site should ensure that the participant understands the instructions.

#### For uncomplicated Grade 1/2 diarrhea

- Stop all lactose-containing products, alcohol and eat frequent small meals that include bananas, rice, applesauce, or toast)
- Stop laxatives, bulk fiber (ie, Metamucil®) and stool softeners (eg, docusate sodium; Colace®)

- Stop high-osmolar food supplements such as Ensure® Plus and Jevity® Plus (with fiber)
- Drink 8 to 10 large glasses of clear liquids per day (eg, water, Pedialyte®, Gatorade® or broth)
- Consider administration of standard dose of loperamide: initial administration 4 mg, then 2 mg every 4 hours (maximum of 16 mg/day) or after each unformed stool
- Discontinue loperamide after 12-hours diarrhea-free (Grade 0) interval
- If uncomplicated Grade 1 to 2 diarrhea persists for more than 24 hours, escalate to high dose loperamide: 2 mg every 2 hours (max. of 16 mg/day) or after each unformed stool.

**Note:** Oral antibiotics may be started as prophylaxis for infections under the discretion of the physician.

- If uncomplicated Grade 1 to 2 diarrhea persists after 48 hours of treatment with loperamide, discontinue loperamide and begin a second-line agent which can be an opiate (opium tincture or paregoric), octreotide acetate or steroid (budesonide).

**For complicated Grade 1/2 diarrhea or any Grade 3 to 4 diarrhea**

- The participant must call the investigator immediately
- If loperamide has not been initiated, initiate loperamide immediately. Initial administration 4 mg, then 2 mg every 4 hours (maximum of 16 mg/day) or after each unformed stool.
- Administer IV fluids and electrolytes as needed. In case of severe dehydration, replace loperamide by octreotide.
- Monitor/continue IV fluids and antibiotics as needed. Intervention should be continued until the participant is diarrhea free for at least 24 hours.
- Hospitalization may need to be considered.

**Skin Toxicity:** Clinical judgment and experience of the treating physician should guide the management plan of each participant. In general, the following interventions are in addition to the rash dosing adjustment guidelines in [Table 6](#).

- Prophylaxis of skin toxicity to be initiated 24 hours prior to the first treatment with study drug or later as needed.

- Application of topical agents to the most commonly affected skin areas such as face, scalp, neck, upper chest and upper back.

Topical agents include non-oily sunscreen (para-aminobenzoic acid [PABA] free, SPF  $\geq 30$ , ultraviolet A [UVA]/ultraviolet B [UVB] protection), topical steroids (preferably mometasone cream ie, Elocon®) and topical erythromycin (ie, Eryaknen® or topical pimecrolimus).

**Note:** Topical agents should be applied on a daily basis starting on Day 1 of study treatment or 24 hours prior to the first dose, and more often as needed.

- Possibly oral doxycycline (100 mg daily) for the first 2-3 weeks of study drug administration.

Other effective medications are antihistamines, other topical corticosteroids, other topical antibiotics and low-dose systemic corticosteroids.

The treatment algorithm based on CTCAE grade is as follows:

#### **Mild rash (CTCAE Grade 1)**

- Consider prophylactic rash treatment if not already started.
- Topical or other topical corticosteroid (ie, mometasone cream) and/or topical antibiotic (ie, erythromycin 2%) are recommended.
- The participant should be reassessed within a maximum of 2 weeks or as per investigator opinion.

#### **Moderate rash (CTCAE Grade 2)**

- Use of topical erythromycin or clindamycin (1%) plus topical mometasone or pimecrolimus cream (1%) plus oral antibiotics such as: lymecycline (408 mg QD), doxycycline (100 mg BID) or minocycline (50 to 100 mg QD).
- Although there has been no evidence of phototoxicity or photosensitivity in participants being treated with selumetinib, doxycycline (or minocycline as second-line) should be used with thorough UV protection (ie, avoidance of direct exposure to sunlight, use of sunscreen and sunglasses).
- Use of acitretin is not recommended

## Severe rash (CTCAE Grade 3-4)

### CTCAE Grade 3

- In addition to the interventions recommended for moderate rash, consider oral prednisolone at a dose of 0.5 mg/kg. Upon improvement, taper the dose in a stepwise manner (25 mg for 7 days, subsequently decreasing the dose by 5 mg/day every day).
- Alternatively, in addition to the interventions recommended for moderate rash, consider oral isotretinoin (low doses, ie, 0.3 to 0.5 mg/kg) [Lacouture, M. E., et al 2011].
- Use of acitretin is not recommended.

### CTCAE Grade 4

- Immediately discontinue the participant from study drug and treat the participant with oral and topical medications (see recommendation CTCAE Grade 3).

### Symptomatic Treatment:

- It is strongly recommended that participants who develop rash/skin toxicities receive symptomatic treatment:
  - For pruritic lesions, use cool compresses and oral antihistaminic agents
  - For fissuring, use Monsel's solution, silver nitrate, or zinc oxide cream. If not sufficient use mild steroid ointments or combinations of steroids and antibiotics such as Fucicort®
  - For desquamation, use emollients with mild pH 5/neutral (best containing urea 10%)
  - For paronychia, antiseptic bath and local potent corticosteroids, use oral antibiotics and if no improvement is seen, refer to a dermatologist or surgeon
  - For infected lesions, obtain bacterial and fungal cultures and treat with topical or systemic antibiotics based on sensitivity of culture

## 6.6 Dose Modification (Escalation/Titration/Other)

### 6.6.1 Dose Administration/Escalation

#### 6.6.1.1 Dose Administration (Preparation)

Details on preparation and administration of MK-8353 and selumetinib are provided in the appropriate Pharmacy/Procedures Manual.

## 6.6.2 Definition of Dose limiting Toxicity

All toxicities will be graded using NCI CTCAE v4.0 based on the investigator assessment.

The DLT window of observation will be during Cycle 1. The observation window can be modified to encompass Cycle 1 and 2 (and/or additional cycles).

The occurrence of any of the following toxicities during Cycle 1 will be considered a DLT, if assessed by the investigator to be possibly, probably, or definitely related to study treatment administration.

1. Grade 4 nonhematologic toxicity (not laboratory).
2. Grade 4 hematologic toxicity lasting  $\geq 7$  days, except thrombocytopenia:
  - Grade 4 thrombocytopenia of any duration
  - Grade 3 thrombocytopenia associated with clinically significant bleeding
3. Any nonhematologic AE  $\geq$  Grade 3 in severity should be considered a DLT, with the following exceptions: Grade 3 fatigue lasting  $\leq 3$  days; Grade 3 diarrhea, nausea, or vomiting without use of anti-emetics or anti-diarrheals per SOC lasting  $< 72$  hours; Grade 3 rash without use of corticosteroids or anti-inflammatory agents per SOC.
4. Any Grade 3 or Grade 4 non-hematologic laboratory value if:
  - Clinically significant medical intervention is required to treat the subject, or
  - The abnormality leads to hospitalization, or
  - The abnormality persists for  $\geq 72$  hours.
  - The abnormality is consistent with drug-induced liver injury and meeting the protocol Events of Clinical Interest criteria (see Section 8.4.7)

Exceptions: Clinically nonsignificant, treatable, or reversible laboratory abnormalities including liver function tests, uric acid, etc.

5. Febrile neutropenia Grade 3 or Grade 4:
  - Grade 3 is defined as absolute neutrophil count (ANC) <1000/mm^3 with a single temperature of >38.3 degrees C (101 degrees F) or a sustained temperature of ≥38 degrees C (100.4 degrees F) for more than 1 hour
  - Grade 4 is defined as ANC <1000/mm^3 with a single temperature of >38.3 degrees C (101 degrees F) or a sustained temperature of ≥38 degrees C (100.4 degrees F) for more than 1 hour, with life-threatening consequences and urgent intervention indicated.
6. An elevated AST or ALT laboratory value that is ≥3X the ULN and an elevated total bilirubin laboratory value that is ≥2X the ULN and, at the same time, an alkaline phosphate laboratory value that is <2X the ULN, as determined by the way of protocol-specified laboratory testing or unscheduled laboratory testing.
7. Prolonged delay (>2 weeks) in initiating Cycle 2 due to treatment-related toxicity.
8. Any treatment-related toxicity that causes the participant to discontinue treatment during Cycle 1.
9. Missing >25% of MK-8353 and/or selumetinib doses as a result of drug-related AE(s) during the first cycle.
10. Grade 5 toxicity.
11. Cardiac disorders
  - Absolute decrease in LVEF >10% compared with baseline and the LVEF is below the institution's lower limit of normal
  - Left ventricular systolic dysfunction Grade ≥3
  - Other cardiac disorders Grade ≥3
12. Vascular disorders
  - Hypertension CTCAE Grade ≥3 requiring more than 1 drug or more intensive therapy
  - Grade 4 hypertension

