- If there is a clinical diagnosis of impetigo, or an infection with *Staphylococcus aureus* is confirmed, topical mupirocin may be used. Infected lesions suspected to be treatment-resistant should be cultured. If there is no improvement after 2 weeks of treatment, therapy for the rash should be considered ineffective and discontinued.
- Additionally, oral antihistamines (nonsedative) may also be considered for the treatment of Grade 1 to 3 rashes. Oral steroids may be considered for Grade 3 rash.

Every medication taken by the subject during the trial and the reason for use must be recorded in the electronic case report form (eCRF). Note that the use of any concomitant medication must relate to the documented medical history, prophylaxis, or an AE of the subject.

Subjects will be permitted to receive appropriate supportive care measures as deemed necessary by the treating physician including but not limited to the items outlined below:

- **Diarrhea:** diarrhea should be treated promptly with appropriate supportive care, including loperamide. Subjects should be instructed to begin taking loperamide at the first sign of: 1) poorly formed or loose stool, 2) occurrence of more bowel movements than usual in one day, or 3) unusually high volume of stool. Loperamide should be taken in the following manner: 4 mg at first onset of diarrhea, then 2 mg after each unformed stool. The daily dose of loperamide should not exceed 16 mg/day. Loperamide should be deferred if blood or mucus is present in the stool or if diarrhea is accompanied by fever. In this setting, appropriate diagnostic microbiologic specimens should be obtained to exclude an infectious etiology. Subjects should be also advised to drink liberal quantities of clear fluids to help prevent dehydration. Supportive care according to institutional guidelines in the context of standard of care for diarrhea are permitted (except prohibited medications; see Section 6.5.2).
- **Nausea/vomiting:** nausea and vomiting should be treated aggressively. After an initial occurrence of Grade 2 or higher nausea or vomiting, strong consideration should be given to the administration of prophylactic antiemetic therapy according to standard institutional practice. Subjects should be strongly encouraged to maintain liberal oral fluid intake.

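### The DLT exceptions for Grade 3 diarrhea, nausea, vomiting and rash require that supportive drugs were not used, while Section 6.5.3 directs or recommends those drugs in Cycle 1, so the classification of these events is not well defined

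*Combined protocol and SAP*

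**What the plan says.** Section 6.6.2 counts a Cycle 1 toxicity as a DLT "if assessed by the investigator to be possibly, probably, or definitely related to study treatment administration". Criterion 3 makes every nonhematologic event of Grade 3 or above a DLT, with listed exceptions. Two matter here:

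- Gastrointestinal: "Grade 3 diarrhea, nausea, or vomiting without use of anti-emetics or anti-diarrheals per SOC lasting" under 72 hours.
- Skin: "Grade 3 rash without use of corticosteroids or anti-inflammatory agents per SOC". This one carries no duration limit.

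The supportive-care sections address the same events:

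- **Diarrhea.** Section 6.5.3.1: "Subjects should be instructed to begin taking loperamide at the first sign of" loose stool. Section 6.5.3.2, for complicated Grade 1/2 or any Grade 3-4 diarrhea: "If loperamide has not been initiated, initiate loperamide immediately".
- **Nausea and vomiting.** Section 6.5.3.1: "nausea and vomiting should be treated aggressively". Section 6.5.3.2 gives antiemetics from Grade 1 upward, at the treating physician's discretion.
- **Rash.** The skin-toxicity part of Section 6.5.3.2 lists topical steroids among its prophylactic agents and says: "Topical agents should be applied on a daily basis starting on Day 1 of study treatment or 24 hours prior to the first dose". A neighboring bullet allows a later start as needed. Section 6.5.3.1 recommends adding topical steroids once rash reaches Grade 3. Section 6.5.3.2 asks that oral prednisolone be considered at Grade 3.

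Section 6.5.3.1 defers only the anemia measures and colony-stimulating factors until after the first cycle. None of the drugs listed above is deferred.

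**The concern.** The exceptions turn on the absence of drugs that the same protocol tells sites to give, or recommends, in the same cycle. A participant treated as directed loses the exemption; one left untreated keeps it. Criterion 3 also leaves *use* undefined. It could mean any exposure, exposure before the event reached Grade 3, or treatment afterward, with prophylaxis counted or not.

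DLT incidence is the primary safety endpoint (Section 9.4.2), and the DLT count drives every Table 2 decision. Classification is made by investigators at multiple sites, and the Synopsis lists no clinical adjudication committee. If the rule can be read in more than one way, the same clinical course can be counted differently, and the count reflects supportive care as well as dose.

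**Working it through.** **1. Classification under two readings.** The table covers Cycle 1 events judged related, where no other DLT criterion applies.

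| Grade 3 event | *Use* at any time | *Use* before onset only |
|---|---|---|
| Diarrhea <72 h, no loperamide | exempt | exempt |
| Diarrhea <72 h, loperamide started at Grade 3 (as 6.5.3.2 directs) | DLT | exempt |
| Diarrhea <72 h, loperamide from first loose stool (as 6.5.3.1 directs) | DLT | DLT |
| Rash, no steroid or anti-inflammatory agent | exempt | exempt |
| Rash, topical steroid added at Grade 3 (as 6.5.3.1 recommends) | DLT | exempt |
| Rash, topical steroid prophylaxis from Day 1 | DLT | DLT |

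If prophylaxis is not counted as use, the last row depends on what was given after onset. Under the literal first column, every row managed with the drugs in Section 6.5.3 is a DLT and only the untreated rows are exempt.

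**2. Reproducing Table 2.** Inputs from Section 4.3.4: target 30%, Beta(1,1) prior, ε1 = ε2 = 0.03. The posterior is Beta(1+x, 1+n−x). For each of (0, 0.27), (0.27, 0.33) and (0.33, 1), divide the posterior probability by the interval width. The largest value gives E, S or D. DU applies if P(p > 0.30) > 0.95; the 0.95 cutoff is not stated and is assumed.

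| DLTs/n | E mass | S mass | D mass | P(p>0.30) | Decision |
|---|---|---|---|---|---|
| 0/3 | 2.652 | 1.375 | 0.301 | 0.240 | E |
| 1/3 | 1.096 | 1.760 | 0.893 | 0.652 | S |
| 2/3 | 0.233 | 0.756 | 1.331 | 0.916 | D |
| 2/4 | 0.466 | 1.321 | 1.187 | 0.837 | S |
| 3/4 | 0.077 | 0.380 | 1.427 | 0.969 | DU |

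All 114 cells of Table 2 reproduce. One reclassified event moves 0/3 to 1/3 (E to S), 1/3 to 2/3 (S to D), or 2/4 to 3/4 (S to DU).

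**3. Illustrative size.** The documents give no Grade 3 rates, so these are assumptions: other-cause DLT probability b = 0.15, excepted-type event probability g = 0.05, 0.10 or 0.20, independent of each other. If all excepted-type events are exempt, the counted rate is b. If none are, it is 1 − (1−b)(1−g). By Table 2, the probability of E is (1−p)³ at n = 3 and P(X ≤ 1) at n = 6.

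| g | Counted rate p | P(E), n=3 | P(E), n=6 |
|---|---|---|---|
| all exempt | 15.0% | 61.4% | 77.6% |
| 5%, none exempt | 1 − 0.85×0.95 = 19.3% | 52.7% | 67.4% |
| 10%, none exempt | 1 − 0.85×0.90 = 23.5% | 44.8% | 57.0% |
| 20%, none exempt | 1 − 0.85×0.80 = 32.0% | 31.4% | 37.8% |

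**4. What the other criteria already catch.** On 4 days on/3 days off, BID, Cycle 1 has 3 × 4 × 2 = 24 doses per drug, consistent with 6000 mg at 250 mg in Section 4.3.2. Criterion 9 makes missing more than 25% of doses for a drug-related event a DLT. Table 7 interrupts both drugs for Grade 3 rash until Grade 1 or lower. Missing one 4-day block is 8/24 = 33%, already a DLT. Missing three dosing days is 6/24 = 25%, which does not exceed the limit.

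**The case against.** The strongest reply is that *per SOC* carries the meaning: Grade 3 despite standard supportive care is dose-limiting, and Grade 3 before such care is not. Dependence on supportive care would then be intended. This is a plausible reading, but criterion 3 does not state it. In particular, the text does not settle how to class a Grade 3 event first treated after onset that resolves within 72 hours. Read literally it is a DLT; on the intended reading it is exempt.

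Other parts of the reply stand and limit the point:

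- A reader might infer that DLT status depends on supportive care *instead of* dose. It does not. Reaching Grade 3 still depends on dose, Grade 4 events are DLTs regardless, and the gastrointestinal exception also has its 72-hour limit.
- A reader might infer that the main effect is a contrast between sites that use skin prophylaxis and sites that do not. Section 6.5.3.1 recommends topical steroids for Grade 3 rash at every site, so on the literal reading most such rashes lose the exemption either way.
- A reader might infer that an untreated Grade 3 rash can persist without ever becoming a DLT. Criteria 7 to 9 catch many persistent rashes.
- Section 4.3.3 describes rash as the most common signal from about day 7, but also says within 3 months, and does not specify Grade 3. It does not show how many Grade 3 rashes fall in the 21-day window.
- Some supportive care is discretionary or offered as guidance, so the exceptions are not strictly empty. That same discretion allows classification to vary.

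**Conclusion.** The conflict between criterion 3 of Section 6.6.2 and Sections 6.5.3.1 and 6.5.3.2 is real and in the current text. A participant managed as directed largely cannot meet the exceptions, and *use* is undefined. The consequence is that classification depends on care and interpretation as well as dose, mainly toward over-counting DLTs when the guidance is followed.

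The effect on a single decision is certain: one event can change the Table 2 outcome. The effect on rates is illustrative only. A spread of 15% against 19-32% rests on assumed event rates and independence, and compares all events exempt with none exempt, so it is an upper bound. It should not be read as an estimated bias in the maximum tolerated dose. Criteria 7 to 9 reduce it for rash. They do not remove it for short gastrointestinal events or for rash costing few doses. For example, Table 7 interrupts dosing for Grade 3 nausea only when optimal antiemetics fail, so a controlled event need cause no missed dose and is classed by criterion 3.

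**What to change.** The sponsor should reconcile criterion 3 of Section 6.6.2 with Sections 6.5.3.1 and 6.5.3.2, so that an event managed as the protocol directs has one unambiguous DLT classification. The wording should state whether *use* refers to the period before onset, after onset or both, and whether prophylactic or instructed medication counts. The clinical content of the exceptions, including whether any duration limit applies to rash, is for the sponsor and investigators to decide. The cost is rewording one criterion; Table 2 and the design parameters are unaffected.

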### 13. Eye disorders

#### Retinal:

- Retinopathy or retinal detachment Grade  $\geq 2$ , confirmed by ophthalmic examination
- Retinal vein disorder including retinal vein occlusion, confirmed by ophthalmic examination

#### Visual disturbances without ocular (retinal) changes:

- Blurred vision, flashing lights, floaters: Grade  $\geq 3$

#### Other specify:

- Grade 4 confirmed by ophthalmic examination

### 6.6.3 Timing of Dose Administration

#### 6.6.3.1 Timing of Administration for MK-8353 and Selumetinib

Participants should be instructed to take MK-8353 and selumetinib capsules  $12 \pm 2$  hours apart for BID dosing schedule with a large glass of water (~250 mL) in the morning and in the evening at approximately the same time every day. (If dosing is changed to QD, participants should be instructed to take MK-8353 and selumetinib capsules every  $24 \pm 2$  hours in the morning). Starting on Day 1 of Cycle 1, MK-8353 and selumetinib will be administered 4 days on/3 days off concomitantly at the same time. On clinic days when PK samples are scheduled, dosing should be delayed until arrival at the clinic and until the pre-dose PK sample has been taken.

The reason for any variability in administration of MK-8353 and selumetinib outside of the protocol specified window should be documented in the subject's chart and recorded on the electronic Case Report Forms (eCRFs).

Every effort should be made to begin the first dose of study intervention on the day of treatment assignment, but if this is not achieved, study intervention should be initiated no later than 3 days from the date of treatment assignment. All subsequent cycles of study intervention may be administered up to 3 days before or 3 days after the scheduled Day 1 of each cycle due to administrative reasons per the investigator's judgment. All study interventions will begin on Day 1 of each cycle after all predose study procedures and assessments have been completed as detailed in Section 2, Summary of Activities.

The Pharmacy Manual contains specific instructions for administration of MK-8353 and selumetinib and additional guidance (for example, missed doses).

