MK-8353 Pharmacokinetics		X	X			X	X							X	X			
 
• C1D1: Pre-dose samples will be collected (within 24 hours prior to pre-dose). Morning dose(s) should be withheld until sample has been drawn. Post-dose samples will be collected at hours 1 (± 10 minutes), 2 (± 10 minutes), 4 (± 10 minutes), 6 (± 10 minutes), and 1 sample any time between 8 and 12 hours (prior to PM dosing for BID regimen).
 
• C1D4: Pre-dose/trough samples will be collected at time 0 (within -10 minutes prior to pre-dose). Morning dose(s) should be withheld until sample has been drawn. Post-dose samples will be collected at hours 1 (± 10 minutes), 2 (± 10 minutes), 4 (± 10 minutes), 6 (± 10 minutes), and 1 sample any time between 8 and 12 hours (prior to PM dosing for BID regimen).
 
• Additional samples will be collected at C2D1, C2D4, C5D1 and C5D4: Pre-dose/trough: Collect at time 0 (within -10 minutes prior to pre-dose). Morning dose(s) should be withheld until sample has been drawn, and Post-dose: Hours 1 (± 10 minutes) and 4 (± 10 minutes). The exact time of sample collection and time of administration of MK-8353 will be recorded.
 

Study Period: Study Period:	Screening Phase	Treatment Cycles (3-week Cycles)															Notes	
Treatment Cycle (C) / Visit:	Screening (Visit)	C1				C2			C3		C4		C5		C6	C7		C8 and beyond
Collection Timepoint (Study Day [D]):		D1	D 4	D 8	D 15	D1	D 4	D 15	D1	D 15	D1	D 15	D1	D 4	D1	D1		D1
Scheduling Window(Days):	-28 to -1		-1	±3	±3	±3	-1	±3	±3	±3	±3	±3	±3	-1	±3	±3		±3

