#### 4.3.2 Maximum Dose/Exposure for This Study

The maximum dose of MK-8353 for this study will be 250 mg administered orally BID, on a 4 days on followed by 3 days off schedule (maximum 500 mg total per day). The Phase 2 dose for MK-8353 monotherapy is 350 mg BID administered continuously. This will provide a total dose of 6000 mg per 3-week cycle which is less than monotherapy dose per 3-week cycle (14700 mg).

The maximum dose of selumetinib for this study will be 125 mg administered orally BID, on a 4 days on followed by 3 days off schedule (maximum 250 mg total per day). The Phase 2 dose for selumetinib monotherapy is 75 mg BID administered continuously. This will provide a total dose of 3000 mg per 3-week cycle which is less than monotherapy dose per 3-week cycle (3150 mg).

Inhibition of both MEK and ERK may exacerbate toxicity of either inhibitor alone. However, intermittent dosing schedules of both MK-8353 and selumetinib (4 days on followed by 3

days off schedule) is likely to be better tolerated than continuous dosing and short half-lives (approximately 8 hours) would reduce concerns over toxicity while maintain anti-tumor activity [Xue, Y., et al 2017].

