## 6.1 Study Intervention(s) Administered

The study intervention(s) to be used in this study are outlined in [Table 4](#).

Table 4 Study Interventions

Arm Name	Arm Type	Intervention Name	Type	Dose Formulation	Unit Dose Strength(s)	Dosage Level(s)	Route of Administration	Regimen/ Treatment Period/ Vaccination Regimen	Use	IMP/ NIMP	Sourcing
MK-8353 + MK-5618	Experimental	MK-8353	Drug	Capsule	50 mg, 100 mg	50 mg, 100 mg, 150 mg, 200 mg, 250 mg	Oral	BID 4 days on and 3 days off	Experimental	IMP	Provided centrally by Sponsor
MK-8353 + MK-5618	Experimental	MK-5618 (Selumetinib)	Drug	Capsule	25 mg	25 mg, 50 mg, 75 mg, 100 mg, 125 mg	Oral	BID 4 days on and 3 days off	Experimental	IMP	Provided centrally by Sponsor

BID = Twice daily; IMP = Investigational Medicinal Products; NIMP = Non-investigational Medicinal Product

Alternate dose levels, drug administration frequency and dosing schedule (eg, BID vs. once daily [QD], on/off intermittent dosing schedule) may be explored.

All supplies indicated in [Table 4](#) will be provided per the "Sourcing" row depending upon local country operational requirements. Every attempt should be made to source these supplies from a single lot/batch number. The study site is responsible for recording the lot number, manufacturer, and expiry date for any locally purchased product per local guidelines unless otherwise instructed by the Sponsor.

Refer to Section 8.1.8 for details regarding administration of the study intervention.

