#### **8.1.8.1 Timing of Dose Administration**

##### **8.1.8.1.1 MK-8353 Administration**

MK-8353 is an oral medication, and is supplied as hard-shell capsules in strength of 50 mg or 100 mg. Participants should be instructed to take MK-8353 capsule(s) in the morning and in the evening at approximately the same times every day.

MK-8353 will be taken BID for the repeated schedule of 4 days on followed by 3 days off.

The Pharmacy Manual contains specific instructions for MK-8353 storage and administration.

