##### **8.1.8.1.2 Selumetinib Administration**

Selumetinib is an oral medication, and is supplied as hard-shell capsules in strength of 25 mg. Participants should be instructed to take selumetinib capsules in the morning and in the evening at approximately the same times every day. Selumetinib should be taken on an empty stomach; no food or drink other than water for approximately 2 hours prior to dosing and approximately 1 hour after dosing.

Selumetinib will be taken BID in a repeating cycle of 4 days on followed by 3 days off.

The Pharmacy Manual contains specific instructions for MK-5618 (selumetinib) storage and administration.

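### Section 6.6.3.1 lets a later cycle's dosing start up to 3 days early with no minimum off period, which undercuts the 4-on/3-off schedule

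*Combined protocol and SAP*

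**What the plan says.** Section 6.6.3.1 sets the regimen from Cycle 1 Day 1: "MK-8353 and selumetinib will be administered 4 days on/3 days off concomitantly at the same time". The same intermittent schedule stands in Table 4 ("BID 4 days on and 3 days off", for both drugs), in Section 8.1.8.1.1 ("MK-8353 will be taken BID for the repeated schedule of 4 days on followed by 3 days off") and in Section 8.1.8.1.2 ("Selumetinib will be taken BID in a repeating cycle of 4 days on followed by 3 days off").

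Section 6.6.3.1 then adds a tolerance: "All subsequent cycles of study intervention may be administered up to 3 days before or 3 days after the scheduled Day 1 of each cycle". The conditions are an administrative reason and the investigator's judgment. The visible part of the treatment-phase Schedule of Activities (SoA) gives Day 1 of Cycle 2 and of later cycles a ±3-day window.

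The tolerance covers dosing as well as the visit. Section 6.6.3.1 continues: "All study interventions will begin on Day 1 of each cycle after all predose study procedures and assessments have been completed". The SoA pharmacokinetic rows place pre-dose samples on C2D1 and C5D1 and hold that morning's dose until the sample is drawn. A site that moves Day 1 forward therefore moves the first dose forward.

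On the purpose of the schedule, Section 4.3.2 says that intermittent dosing of both drugs "is likely to be better tolerated than continuous dosing". Section 4.3.3 argues from half-lives of about 8 hours that both drugs are cleared within about 2 days of stopping.

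**The concern.** The last off block of a 21-day cycle ends on the day before the next scheduled Day 1, so each day of early start comes out of that block. No visible text keeps a minimum number of off days.

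The off days are part of the sponsor's safety argument. Section 4.3.2 warns that inhibiting both MEK and ERK may worsen the toxicity of either inhibitor, and offers the intermittent schedule as mitigation. Section 4.3.1 counts that schedule as part of the conservative starting approach. Section 4.3.2 also supports the top selumetinib dose by noting that its total per 3 weeks stays below that of continuous monotherapy. An administrative early start weakens both arguments.

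**Working it through.** **Inputs.** 3-week cycles (SoA); 4 days on/3 days off, BID (Section 6.6.3.1, Table 4); early start of up to 3 days (Section 6.6.3.1); top doses 250 mg and 125 mg BID, monotherapy doses 350 mg and 75 mg BID continuously (Section 4.3.2); half-life about 8 h (Sections 4.3.2 and 4.3.3).

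**The plan's own totals.** Dosing falls on Days 1-4, 8-11 and 15-18, which is 12 days per cycle.

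- MK-8353: 250 × 2 × 12 = 6000 mg; monotherapy 350 × 2 × 21 = 14700 mg.
- Selumetinib: 125 × 2 × 12 = 3000 mg; monotherapy 75 × 2 × 21 = 3150 mg.

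All four match Section 4.3.2.

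**Off days.** The break is Days 19-21 and Cycle 2 is due on Day 22. A start k days early leaves (22 − k) − 19 = 3 − k off days. A Day 19 start joins Days 15-18 to Days 19-22: 8 dosing days, or 16 consecutive BID doses.

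**Dose over 21 days from Day 15 (Days 15-35).** Dosing days are counted block by block:

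- Day 22 start: 15-18, 22-25, 29-32 = 12.
- Day 21 start: 15-18, 21-24, 28-31, 35 = 13.
- Day 20 start: 15-18, 20-23, 27-30, 34-35 = 14.
- Day 19 start: 15-18, 19-22, 26-29, 33-35 = 15.

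Multiplying by 250 mg/day (selumetinib) and 500 mg/day (MK-8353):

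| Cycle 2 start | Off days | Longest run | Dosing days, Days 15-35 | Selumetinib at 125 mg BID | MK-8353 at 250 mg BID |
|---|---|---|---|---|---|
| Day 22 (on schedule) | 3 | 4 days | 12 | 3000 mg | 6000 mg |
| Day 21 | 2 | 4 days | 13 | 3250 mg | 6500 mg |
| Day 20 | 1 | 4 days | 14 | 3500 mg | 7000 mg |
| Day 19 | 0 | 8 days | 15 | 3750 mg | 7500 mg |

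Every early start at 125 mg BID passes the 3150 mg comparator. At 100 mg BID even the extreme gives 15 × 200 = 3000 mg, so the comparator is passed only at the top selumetinib dose.

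**Washout.** Hours from the Day 18 evening dose to the first Cycle 2 morning dose = 24 × (start day − 18) − 12, give or take about 2 h under the 12 ± 2 h dosing rule. Assuming simple first-order decay with an 8 h half-life, the fraction left is 2^(−hours/8).

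| Start | Gap | Half-lives | Left at first Cycle 2 dose |
|---|---|---|---|
| Day 22 | 84 h | 10.5 | 0.07% |
| Day 21 | 60 h | 7.5 | 0.55% |
| Day 20 | 36 h | 4.5 | 4.4% |
| Day 19 | 12 h | 1.5 | 35.4% |

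One day early still allows the roughly 2 days (48 h) of elimination that Section 4.3.3 describes. Two days early falls short of it, although little drug remains. Three days early is an ordinary within-day dosing interval.

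**The case against.** The strongest case against is that the plan made a choice. A general schedule followed by a specific, permissive window is most naturally read as a schedule with a tolerance. A late start of 1 to 3 days also departs from 3 days off, giving 4 to 6, and nobody would object to that. This stands. A reader might infer that Section 6.6.3.1 contradicts itself, Table 4 and Sections 8.1.8.1.1 and 8.1.8.1.2, with no rule of precedence. The documents do not support that stronger reading, because the window can be read as qualifying the schedule. What remains is that the early side of the window works against the stated safety rationale and the late side does not.

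The consequence is also narrow. One day early hardly changes washout, and only the extreme removes the break. The evidence in Section 4.3.3 that continuous dosing was toxic comes from a preclinical RAF/MEK/ERK triplet, not from a single 8-day run of this doublet. This also stands: the documents do not show that an early start would cause toxicity.

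It could be said that the per-cycle totals are untouched, since each cycle still has 12 dosing days. That is true of a cycle as labelled, but an early start shortens the calendar span of the cycle before it. Section 4.3.2 states its totals, and the monotherapy comparators, per 3 weeks. Over 21 calendar days the totals are exceeded, so this reassurance fails.

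Finally, Section 6.6.3.1 sends sites to the Pharmacy Manual for administration instructions, and the treatment-phase SoA is only partly visible. Either may already limit early dosing.

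**Conclusion.** The point holds as a weakness in a stated rule. Section 6.6.3.1 and the SoA window permit later cycles' dosing to start up to 3 days early with no minimum off period, leaving 2, 1 or 0 of the 3 off days. At 125 mg BID the selumetinib total over the 21 days from Day 15 exceeds both the plan's own figure and the monotherapy comparator, even at 1 day early. MK-8353 exceeds its 6000 mg figure at 250 mg BID but stays far below 14700 mg, so the comparator argument is affected for selumetinib only.

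The size rests on the preceding cycle having been dosed as scheduled, with its last block on Days 15-18. The washout percentages also rest on first-order decay. How often sites would use the early side cannot be judged from the documents. This is a cheap improvement to make. It does not show that the trial is unsafe or the design invalid.

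**What to change.** In Section 6.6.3.1, change the dosing window for Cycle 2 onward to 0 to +3 days, and state that dosing never starts before scheduled Day 1. Align the SoA: Day 1 dosing and every procedure timed to the dose (PK, pERK, pre-dose ECG, vital signs) take 0 to +3 days, and the −3 day side remains only for assessments not tied to dosing.

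The same sentence should count scheduled Day 1 as 21 days after the previous cycle's actual Day 1, because the visible text does not say how it is counted. If Cycle 2 began 3 days late on Day 25, its last block would be Days 39-42. A Cycle 3 start fixed at Day 43 would then again leave no break.

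The cost is a short edit in 6.6.3.1 and a matching one in the SoA. Sites lose the option of starting a cycle's dosing early, and few Day 1 procedures would still use the early side. The change also keeps Cycle 2 doses out of the 21-day DLT observation period named in Section 6.3.1, so the DLT rules need no edit.
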